7.1.6.2. Incomplete Dates

If the onset date of the AE is incomplete and the AE stop date is not prior to the first dosing date of study drug, then the month and year (or year alone if month is not recorded) of onset determine whether an AE is treatment emergent. The event is considered treatment emergent if both of the following 2 criteria are met:

- The AE onset is the same as or after the month and year (or year) of the date of first dose of study drug, and
- The AE onset date is the same as or before the month and year (or year) of the date corresponding to 30 days after the date of the last dose of study drug

An AE with completely missing onset and stop dates, or with the onset date missing and a stop date later than the date of the first dose of study drug, will be considered to be treatment emergent. In addition, an AE with the onset date missing and incomplete stop date with the same or later month and year (or year alone if month is not recorded) as the first dosing date of study drug will be considered treatment emergent.

7.1.7. Summaries of Adverse Events and Deaths

The number and percentage of subjects who experienced at least 1 TEAE will be provided and summarized by SOC and PT, and by treatment sequence with treatments listed thereunder based on the Safety Analysis Set as follows:

- All TEAEs
- All TEAEs related to study drug
- All TEAEs related to study procedures
- All TEAEs by severity

- TEAEs of Grade 3 or higher
- All TEAEs related to study drug by severity
- All SAEs
- All SAEs related to study drug
- All TEAEs leading to premature discontinuation of study drug
- Death

There will be two ways to summarize AEs:

- 1) Two treatment sequences will be combined. And the same treatment (FIL, ATV, etc.) from different treatment sequence will be pooled together.
- 2) Two treatment sequences will be summarized separately.

A brief, high-level summary of AEs described above will be provided by the number and percentage of subjects who experienced the above AEs and by treatment group and overall total. All deaths observed in the study will also be included in this summary.

Multiple events will be counted only once per subject per treatment in each summary. An AE that starts in one treatment period and continues into the following treatment period(s) will be counted only in the period in which the AE began. Adverse events will be summarized and listed first in alphabetic order of SOC and then by PT in descending order of total frequency within each SOC, and the alphabetic order of PT will be applied within the same frequency. For summaries by grade, the most severe grade will be used for those AEs that occurred more than once in an individual subject per treatment during the study.

In addition to the above summary tables, all TEAEs and SAEs will be summarized by PT only, in descending order of total frequency and the alphabetic order within the same frequency.

In addition, data listings will be provided by subject for the following:

- All AEs (indicating whether the event is treatment emergent)
- SAEs
- Deaths
- AEs leading to premature discontinuation of study drug

7.1.8. Additional Analysis of Adverse Events

No additional analysis of adverse events is planned.

7.2. Laboratory Evaluations

Laboratory data collected during the study will be analyzed and summarized using both quantitative and qualitative methods. Summaries of laboratory data will be provided for the Safety Analysis Set and will include data collected up to the last dose of study drug plus 30 days for subjects who have permanently discontinued study drug. The analysis will be based on values reported in conventional units. When values are BLQ, the imputed value will be used for the purpose of calculating summary statistics. If a lab value is reported using a non-numeric qualifier (eg, less than (<) a certain value, or greater than (>) a certain value), the given numeric value will be used in the summarization and will be listed. Both of them will be listed as such.

The Incidence of treatment-emergent graded laboratory abnormalities will be summarized by treatment sequence with treatments listed thereunder.

A by-subject listing for laboratory test results will be provided by subject ID number and time point in chronological order for hematology, serum chemistry (fasting) and urinalysis separately. Values falling outside of the relevant reference range and/or having a severity grade of 1 or higher on the Gilead Grading Scale for Severity of Adverse Events and Laboratory Abnormalities and treatment emergent graded laboratory abnormalities will be flagged in the data listings, as appropriate.

Listings by subjects for Serum pregnancy test (females of childbearing potential only), Hepatitis B virus (HBV), hepatitis C virus (HCV), human immunodeficiency virus type 1 testing (HIV-1), Follicle Stimulating Hormone (FSH), Thyroid stimulating hormone testing (screening only), and Urine drug and alcohol assessments at screening will also be provided.

Separate by-subject listing of treatment-emergent laboratory abnormalities and treatment-emergent grade 3 or higher laboratory abnormalities will be provided by subject ID number and visit in chronological order. These listing will include all test results that were collected throughout the study for the laboratory test(s) of interest, with all applicable severity grades displayed.

No inferential statistics will be generated.

7.2.1. Summaries of Numeric Laboratory Results

Descriptive statistics will be provided by treatment sequence for all laboratory test specified in the study protocol as follows:

- Predose values
- Values at each postdose scheduled time point
- Change from predose at each postdose scheduled time point

Predose and postdose values will be defined as described in Section 3.4. Change from predose to a postdose visit will be defined as the visit value minus the predose value. The mean, median, Q1, Q3, minimum, and maximum values will be displayed to the reported number of digits; SD values will be displayed to the reported number of digits plus 1.

In the case of multiple values in an analysis window, data will be selected for analysis as described in Section 3.4.2.

7.2.2. Graded Laboratory Values

The CTCAE Version 5.0 will be used to assign toxicity grades (0 to 4) to laboratory results for analysis. Grade 0 includes all values that do not meet the criteria for an abnormality of at least Grade 1. For laboratory tests with criteria for both increased and decreased levels, analyses for each direction (ie, increased, decreased) will be presented separately.

7.2.2.1. Treatment-Emergent Laboratory Abnormalities

Treatment-emergent laboratory abnormalities are defined as values that increase at least 1 toxicity grade from predose at any postdose time point, up to and including the date of last dose of study drug plus 30 days for subjects who permanently discontinued study drug. If the relevant predose laboratory value is missing, any abnormality of at least Grade 1 observed within the time frame specified above will be considered treatment emergent.

7.2.2.2. Summaries of Treatment-emergent Laboratory Abnormalities

The following summaries (number and percentage of subjects) for treatment-emergent laboratory abnormalities will be provided by lab test and by treatment sequence with treatments under the treatment sequence; subjects will be categorized according to the most severe postdose abnormality grade for a given lab test within a treatment:

- Treatment-emergent graded laboratory abnormalities
- Treatment-emergent grade 3 or higher laboratory abnormalities

There will be two ways to summarize treatment-emergent laboratory abnormalities:

- 3) Two treatment sequences will be combined. And the same treatment (FIL, ATV, etc.) from different treatment sequence will be pooled together.
- 4) Two treatment sequences will be summarized separately.

For all summaries of laboratory abnormalities, the denominator is the number of subjects with nonmissing postdose values up to 30 days after last dosing date.

7.2.3. Liver-Related Laboratory Evaluations

Liver-related abnormalities after initial study drug dosing will be examined and summarized using the number and percentage of subjects who were reported to have the following laboratory test values for postdose measurements:

- Aspartate aminotransferase (AST): (a) > 3 times of the upper limit of reference range (ULN); (b) $> 5 \times$ ULN; (c) $> 10 \times$ ULN; (d) $> 20 \times$ ULN
- Alanine aminotransferase (ALT): (a) $> 3 \times$ ULN; (b) $> 5 \times$ ULN; (c) $> 10 \times$ ULN; (d) $> 20 \times$ ULN
- AST or ALT: (a) $> 3 \times$ ULN; (b) $> 5 \times$ ULN; (c) $> 10 \times$ ULN; (d) $> 20 \times$ ULN
- Total bilirubin: $> 2 \times$ ULN
- Alkaline phosphatase (ALP) $> 1.5 \times$ ULN
- AST or ALT $> 3 \times$ ULN and total bilirubin: (a) $> 1.5 \times$ ULN; (b) $> 2 \times$ ULN

The summary will be provided by treatment sequence with treatments listed thereunder.

There will be two ways to summarize liver-related laboratory abnormalities:

- 5) Two treatment sequences will be combined. And the same treatment (FIL, ATV, etc.) from different treatment sequence will be pooled together.
- 6) Two treatment sequences will be summarized separately.

The summary will include data from all postdose visits up to 30 days after the last dose of study drug. For individual laboratory tests, subjects will be counted once based on the most severe postdose values. For both the composite endpoint of AST or ALT and total bilirubin, subjects will be counted once when the criteria are met at the same postdose visit date. The denominator is the number of subjects in the Safety Analysis Set who have nonmissing postdose values of all relevant tests at the same postdose visit date. A listing of subjects who met at least 1 of the above criteria will be provided.

7.3. Body Weight, Height, BMI, and Vital Signs

Descriptive statistics will be provided by treatment sequence for body weight, BMI, and vital signs as follows:

- Predose value
- Values at each postdose at scheduled time point
- Change from predose at each postdose scheduled time point

In addition, descriptive statistics will be provided by treatment sequence for height at baseline only.

Predose and postdose values will be defined as described in Section 3.4. Change from predose to a postdose visit will be defined as the postdose value minus the predose value.

In the case of multiple values in an analysis window, data will be selected for analysis as described in Section 3.4.2. No inferential statistics will be generated.

A by-subject listing of vital signs will be provided by subject ID number and time point in chronological order. Body weight, height, and BMI will be included in the vital signs listing, if space permits, otherwise they will be provided separately.

7.4. Prior and Concomitant Medications

Medications collected at screening, admission (Day -1) and during the study will be coded using the BMAR20 version of the World Health Organization (WHO) Drug dictionary.

A summary of prior and concomitant medications will not be provided.

All prior and concomitant medications (other than per-protocol study drugs) will be provided in a by-subject listing sorted by subject ID number and administration date in chronological order.

7.5. Electrocardiogram Results

Electrocardiogram (ECG) data will not be presented in the CSR since ECGs were not assessed in this study other than as part of the screening process for potential new subjects.

A by-subject listing for ECG assessment results will be provided.

7.6. Other Safety Measures

By-subject listings for creatine clearance test results and physical examination findings during the study will be provided by subject ID number.

Although not necessarily related to safety, a by-subject listing of all comments received during the study on the comments form will be provided by subject ID number, and form for which the comment applies.

7.7. Changes From Protocol-Specified Safety Analyses

If any of below events related to COVID-19 occurs, a by-subject listing may be provided by subject identification (ID) number in ascending order to show:

- Reasons for premature study drug or study discontinuation due to COVID-19
- Important protocol deviations related to COVID-19
- AEs related to COVID-19

Premature study drug or study discontinuation due to COVID-19 is identified either with reason of AE, and AE is COVID-19 related, or with reason of other than AE, and description contains key word “COVID”.

IPD related to COVID-19 is identified by searching description with key word “COVID”.

AE’s related to COVID-19.

Vital sign will only be summarized by treatment sequence, not treatment.

Electrocardiogram assessments will not be summarized by treatment or treatment sequence, as they will only be performed as part of the screening process.

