8.1.3. Secondary Endpoint

The secondary endpoints of this study are as follows:

- Incidences of AEs
- Laboratory abnormalities
- Vital signs

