8.5.4. Other Safety Evaluations

Vital signs and ECG data will be summarized by treatment/treatment sequence..

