2.4. Changes from Protocol-Specified Analysis

No changes from protocol-specified analyses are planned.

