3.4.2. Analysis Window

The nominal visit as recorded on the CRF will be used when data are summarized by visit. Any data relating to unscheduled visits will not be assigned to a particular visit or time point and in general will not be included in summaries but will be listed in the listings. However, the following exceptions will be made:

- An unscheduled visit prior to the first dose of study drug may be included in the calculation of predose value, if applicable.
- For subjects who prematurely discontinue from the study, ET data will be summarized as a separate visit, labeled ‘Early Termination Visit.’
- For laboratory abnormalities, all postdose values (including scheduled and unscheduled visits) will be used to assess the maximum toxicity.
- For vitals assessments, all postdose values (including scheduled and unscheduled visits) will be used to assess maximum postdose and maximum postdose change.

3.4.3. Selection of Data in the Event of Multiple Records on the Same Day

Depending on the statistical analysis method, single values may be required for each day. For example, change from predose by visit usually requires a single value.

If multiple valid, non-missing numeric observations exist on a day, records will be chosen based on the following rules if a single value is needed:

- For predose, the last available record on or prior to the date and time of the first dose of study drug will be selected. If there are multiple records with the same time or no time recorded on the same day, average (arithmetic or geometric mean, as appropriate) will be used for the predose value.
- For postdose values:
 - The record closest to the nominal day for that visit will be selected.
 - If there are 2 records that are equidistant from the nominal day, the later record will be selected.
 - If there is more than 1 record on the selected day, the average will be taken, unless otherwise specified.
 - If multiple, valid, non-missing categorical observations exist on a day, records will be chosen based on the following rules if a single value is needed:

- For predose, the last available record on or prior to the date and time of the first dose of study drug will be selected. If there are multiple records with the same time or no time recorded on the same day, the value with the lowest severity will be selected (e.g., normal will be selected over abnormal for safety ECG findings).

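### Vital signs, a secondary endpoint, have no planned summary pooled by treatment, and the overall-extreme rule names a maximum but no minimum

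*SAP*

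**What the plan says.** Protocol 8.1.3 lists vital signs among three secondary endpoints, with adverse events and laboratory abnormalities. For their presentation, Protocol 8.5.4 states: "Vital signs and ECG data will be summarized by treatment/treatment sequence". Protocol 8.5 adds a general rule that safety data are summarised by treatment, according to the drug received.

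The SAP narrows this. SAP 7.3 states: "Descriptive statistics will be provided by treatment sequence for body weight, BMI, and vital signs as follows". The items listed there are the predose value, the value at each scheduled visit and "Change from predose at each postdose scheduled time point". The change is signed: "Change from predose to a postdose visit will be defined as the postdose value minus the predose value". SAP 7.7 confirms the departure: "Vital sign will only be summarized by treatment sequence, not treatment". The sentence after it drops the ECG summary and explains why (ECGs are done at screening only). No reason is given for vital signs. SAP 2.4, meanwhile, says "No changes from protocol-specified analyses are planned".

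SAP 3.4.2 leaves unscheduled readings out of summaries in general. For vital signs it makes one exception: "all postdose values (including scheduled and unscheduled visits) will be used to assess maximum postdose and maximum postdose change". No minimum is named, the rule is not set within treatment, and SAP 7.3 lists no table that uses it.

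For adverse events (SAP 7.1.7), graded laboratory abnormalities (7.2.2.2) and liver tests (7.2.3), the SAP plans two presentations: sequences separate, and the same treatment pooled across sequences. Vital signs get only the first.

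**The concern.** Both sequences receive Treatment A (statins alone) and Treatment B (filgotinib with statins). Sequence is an order of treatments, so a table with sequence as its only column factor does not line up A against B. The secondary objective concerns the safety and tolerability of filgotinib, alone or with the probe drugs, and the natural display for it is by treatment over the whole sample. The SAP provides this for the other safety endpoints but not for vital signs, and does not say why.

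The overall-extreme rule raises a second issue. Blood pressure, heart rate, respiration rate and temperature can be abnormal in either direction. A rule that keeps only the largest value and the largest signed change describes rises. It also covers the whole post-dose period, so it mixes time on A with time on B.

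**Working it through.** The plan states no numerical figure on this point, so the check is of text and schedule, with some supporting arithmetic.

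**1. Scheduled vital-sign days by treatment** (Protocol Tables 6-1 and 6-2, and the dosing table in Protocol 5.4)

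| Sequence | Treatment A and its follow-up | Treatment B |
|---|---|---|
| AB | Days 1, 3; Day 6 (washout, 72 h after pravastatin/rosuvastatin) | Days 7, 10, 12, 14, 15, 17 |
| BA | Days 18, 20; Day 23 (72 h after pravastatin/rosuvastatin) | Days 1, 3, 6, 7, 8, 9, 11 |

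Within a sequence, every scheduled visit belongs to one treatment or its washout, so the by-visit tables do separate days on filgotinib from days off it.

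**2. What cannot be read across sequence columns.** The post-dose days common to both sequences are 1, 3, 6 and 7. In AB versus BA they pair atorvastatin with filgotinib, pravastatin/rosuvastatin with filgotinib, washout with filgotinib plus atorvastatin, and the first filgotinib dose with the seventh. None of these is B against A for the same probe.

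**3. Matched days exist.**

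| Event | AB: A | AB: B | BA: A | BA: B |
|---|---|---|---|---|
| Atorvastatin day | 1 | 12 | 18 | 6 |
| Pravastatin/rosuvastatin day | 3 | 14 | 20 | 8 |
| 72 h after pravastatin/rosuvastatin | 6 | 17 | 23 | 11 |

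**4. What pooling adds.** SAP 8.1.4 reports 25 evaluable participants, 12 in one sequence and 13 in the other. With equal SDs, the standard error of a mean scales as 1/√n:

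- √(25/12) = 1.44
- √(25/13) = 1.39

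Within one sequence, B minus A also carries any period difference. Without carryover, AB estimates (treatment effect + period difference) and BA estimates (treatment effect − period difference). Pooling 12 and 13 leaves (13 − 12)/25 = 0.04 of the period difference.

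**5. What the planned tables would show if there were a fall.** A simulation used the schedule in step 1 with 13 participants per sequence. Its inputs are assumptions, not figures from the documents: independent normal readings, a within-participant SD of 4, 6 or 8 units, and a true fall of 0 or 10 units throughout Treatment B. With the fall, the by-visit mean change is about −10 at every B visit and about 0 at every A visit, in both sequences. The mean per-participant extremes in Sequence AB are:

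| Within-participant SD | Maximum change: no fall → fall of 10 | Minimum change: no fall → fall of 10 |
|---|---|---|
| 4 | +5.9 → +3.4 | −5.9 → −15.1 |
| 6 | +8.9 → +5.4 | −8.9 → −17.7 |
| 8 | +11.9 → +7.6 | −11.9 → −20.3 |

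Results for BA are similar. The fall is visible by visit. The maximum stays positive and does not show it as a fall, whereas the minimum moves by 8 to 9 units.

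**6. A limit on extremes by treatment.** Treatment B has 6 or 7 scheduled readings; Treatment A has 2 or 3, depending on whether the 72 h visit is counted. For independent, equal-variance normal readings, the expected extreme is about 0.85 SD over 3 readings, 1.27 SD over 6 and 1.35 SD over 7. With no drug effect, B would look more extreme than A by 1.27 − 0.85 = 0.42 SD or 1.35 − 0.85 = 0.50 SD.

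**The case against.** A reader might infer that no table shows a treatment effect and that a fall in blood pressure or heart rate would be missed. The documents do not support either reading. The by-visit tables within each sequence separate the treatments in the same participants and show signed change. SAP 3 requires quartiles and the minimum for continuous variables. The maximum rule in SAP 3.4.2 does not govern those tables, and every reading is listed by participant.

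A reader might also infer that a participant who feels faint and has an unscheduled low reading would leave no trace in any summary. That fails too. Protocol 7.6 requires abnormal assessments, vital signs among them, to be recorded as adverse events when they accompany signs or symptoms and meet the definition. SAP 7.1.7 summarises such events with treatments pooled across sequences. Only the numeric value of the reading is confined to the listings.

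The protocol's slash can also be read as either/or, and Protocol 8.5.3 itself presents numeric laboratory results by sequence. That is a fair precedent. Against it, Protocol 8.5 calls for safety data by treatment, and SAP 7.7 itself records the narrowing as a change from the protocol.

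Finally, the tables are descriptive and no test or decision depends on them, so the 1.4 ratio measures clarity of display, not lost power. This stands and limits the weight of the point.

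**Conclusion.** The point holds in a limited form. The SAP removes the by-treatment part of a protocol-specified summary for a secondary safety endpoint, gives no reason, and contradicts itself between 2.4 and 7.7. Treatment remains readable within each sequence, on 12 or 13 participants, but no vital-signs table brings the 25 together by treatment. The overall-extreme rule covers one direction only, so each participant's lowest value and the number behind an unscheduled low reading must be sought in the listings.

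The cost is a standard error 1.39 to 1.44 times larger for a by-visit mean (equal SDs assumed), a within-sequence contrast mixed with period, and no summary of participant-level lows. Two limits apply to any reading by treatment, planned or added. The documents do not state when vital signs are taken relative to dosing, so some dosing-day readings may be predose. Change is measured from one study-level predose value (SAP 3.4.1), so Period 2 change is not measured from the start of that period. The primary pharmacokinetic conclusion is untouched.

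**What to change.** 1. In SAP 7.3 and 7.7, add a descriptive vital-signs summary by treatment, sequences pooled, at the matched days: AB Days 1/3/6 (A) versus 12/14/17 (B), and BA Days 18/20/23 (A) versus 6/8/11 (B). State in a footnote that change is from a single study-level predose value, and give the timing of the readings relative to dose if it was recorded. A within-participant B minus A difference at matched days would avoid the first issue, since the common predose value cancels.

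2. In SAP 3.4.2 and 7.3, report the minimum as well as the maximum post-dose value and change, including unscheduled readings, and name the table that holds them. Where extremes are shown by treatment, restrict the scheduled readings to the matched days and show unscheduled readings separately. Otherwise Treatment B looks more extreme only because it has more readings.

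3. Reconcile SAP 2.4 with 7.7, and give the reason if the by-sequence-only choice is kept.

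The cost is a few lines of SAP text and one or two descriptive tables from data already collected, with no added measurements. If the SAP is already final, its Section 1 allows the change to be documented in the clinical study report.
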